## STUDY SUMMARY

Title	Comparison of Sleep Apnea Assessment Strategies to Maximize TBI Rehabilitation Participation and Outcome (C-SAS)
Methodology	Prospective, diagnostic clinical trial
Study Duration	Study recruitment was initiated on 05/2017 and completion of all participants in the protocol occurred on 02/2019.
Study Centers	Potential participants were consecutive patients enrolled in the TBI Model Systems (TBIMS) at six sites (Tampa, FL [James A. Haley Veterans Hospital]; Seattle, WA [University of Washington]; Dallas, TX [Baylor Scott & White Rehabilitation]; Columbus, OH [Ohio State University]; Denver, CO [Craig Hospital]; and Philadelphia, PA [Moss Rehabilitation Institute]).
Objectives	
Aim 1: For individuals with TBI, determine comparative effectiveness of AASM endorsed patient-reported screening tools and objective actigraphy to identify those at high risk of sleep apnea as diagnosed through Level 1 Diagnostic Polysomnography.
 
Aim 2: Determine the diagnostic accuracy (non-inferiority of Level 3 portable diagnostic testing in determining presence of sleep apnea in patients with acute TBI patients in the rehabilitation setting.

Number of Subjects	
Aim 1: 248
 
Aim 2: 214

Diagnosis and Main Inclusion Criteria	
Inclusion Criteria:
 
 
*Damage to brain tissue caused by an external mechanical force
 
*Alteration of consciousness > 24 hours, or loss of consciousness > 30 minutes, or Glasgow Coma Scale (GCS) score in the Emergency Department of 3-12, or intracranial abnormalities on imaging regardless of GCS
 
*Admission to inpatient rehabilitation
 
*Minimum age 16 years at civilian sites and 18 years at the VA site
 
*Consent to participate by person with brain injury (if able), family member or legally authorized representative into the TBI Model System lifetime study. This criterion was relaxed in Study Month 11.
 

	
Exclusion Criteria:
 
 
*Habitual sleep duration > 2 hours/night for two (2) consecutive nights not being established prior to PSG
 
*Presence of a physical deformity precluding sensitivity of PSG instrumentation (i.e. full body cast, PSG that could not be removed prior to PSG)
 
*Medical instability as determined by the treating physician (i.e. agitation, acute illness)
 
*Infeasibility of tracheostomy placement with decannulation or overnight capping during rehabilitation
 

Study Product
	
Aim1: Subjects will complete paper and pencil screening tests (STOPBang, Berlin, MAPI), actigraphy, and Level 1 Diagnostic Polysomnography.
 
Aim 2: Subjects recruited will undergo simultaneous administration of Level 1 Diagnostic Polysomnography and Level 3 Portable Diagnostic tests.

Statistical Methodology
	
Aim 1: Area under the curve (AUC) of screening tools predicting sleep apnea status and severity.
 
Aim2: Non-inferiority of Level 3 portable diagnostic tests to the criterion standard, Level 1 Polysomnography.

**Purpose:**

The primary objective is to identify the comparative effectiveness of existing screening and diagnostic tools for sleep apnea to promote earlier detection (thus treatment) during inpatient rehabilitation for moderate to severe traumatic brain injury (TBI).

**Background:**

Given that sleep is critical for neural repair and disordered sleep may play a role in slowing functional recovery and prolonging rehabilitation, early detection of sleep apnea is critical (Stakeholder Input). The Agency for Healthcare Research and Quality's (AHRQ) Comparative Effectiveness Review highlighted insufficient comparative effectiveness evidence for sleep apnea diagnostic and screening tools. This is a prospective, observational cohort study conducted on inpatient rehabilitation units at six Traumatic Brain Injury (TBI) TBI Model System sites. The diagnostic utility of existing sleep studies is needed to inform clinical management during acute recovery from TBI.

**Goals of the Study:**

(Aim 1: Screening) For individuals with TBI, determine comparative effectiveness of the American Academy of Sleep Medicine (AASM) endorsed screening tools and objective actigraphy (ACG) to identify those at high risk of sleep apnea as diagnosed through Level 1 polysomnography (PSG) which is the criterion standard. (Aim 2: Diagnosis). Determine the diagnostic accuracy (non-inferiority) of portable diagnostic testing (more accessible test) relative to Level 1 PSG (laboratory-quality study; criterion standard, less accessible test) in determining presence of sleep apnea in patients with acute TBI during inpatient rehabilitation hospitalization.

**Duration of the Study:**

The study completed enrollment and met recruitment goals within a 19-month period. Participants completed study activities upon completion of diagnostic testing.

**Product Description and Intended Use:****Sleep Apnea Screening Tools (comparators)**

STOPBANG (OSA Screening Comparator). The STOPBANG is comprised of eight (8) items that refer to Snoring, Tiredness, Observed breathing pauses during sleep, treatment for high blood Pressure, elevated Body mass index, older Age, wide Neck circumference, and male Gender. An affirmative response to 2 items indicates low risk, 3-4 items intermediate risk, 5-8 items high risk.

Berlin (OSA Screening Comparator). The Berlin Questionnaire is a 10-item measure that evaluates risk factors for sleep apnea into three (3) categories (snoring severity, excessive daytime sleepiness and history of high blood pressure or obesity). Positivity in two or more of these categories is associated with a high likelihood of clinically-relevant sleep apnea.

Multivariate Apnea Prediction Index (MAPI; OSA Screening Comparator). The questionnaire consists of three breathing-related questions and utilizes information on demographics (sex, weight, height, age), from which a probability of having sleep apnea (0-100%) can be calculated.

Actigraphy (ACG; Comparator). A wrist-worn accelerometer (Actiwatch Spectrum, Philips/Respironics, Bend, OR) was used to document sleep metrics during the trial. Activity data informing sleep statistics were recorded in 15-second intervals.

**Diagnostic Comparators**

Level 1 Polysomnography (gold standard method) is the criterion standard for diagnosing sleep apnea with overnight monitoring conducted routinely in a sleep laboratory with a registered polysomnography technician in attendance to assure quality of the study through monitoring of data collection using computer interfaces. All sites utilized a uniform system which for this trial was the Philips Alice 6 LDx Diagnostic Sleep System with results scored in and generated by the Philips Sleepware G3 version 3.8.1 software. The Alice has the capability for up to 55 channels of information collected during overnight monitoring to diagnose sleep disorders including 19 EEG (electroencephalography) inputs, 5 dedicated EMG (electromyography) channels, 3 Chin EMG inputs, EOG (ocular) channels and 7 ECG (heart) channels. Additional features include measurement of thermal flow, snoring, body position, actimeter inputs, light sensors, pulse oximetry, chest and abdominal effort with 8 AUC inputs, and video and audio integration. Many devices are available on the market. Clinician stakeholders on the study (with no conflicts of interest) recommended the system chosen for study purposes.

Portable Sleep Studies (comparator for non-inferiority) are also known as home sleep apnea tests (HSATs in the sleep medicine field). The portable sleep study device used in this trial was the Nox T-3 Monitor [Nox Medical Inc., Reykjavik, Iceland] and Noxturnal version 4.4.2 software. This device used a total of four channels for assessment of sleep apnea including chest and abdominal effort (2), thermal flow (1), and pulse oximetry (1) along with audio recording of snoring. It does not utilize electroencephalography data to determine sleep states which is included in the scoring of sleep apnea using the criterion standard test, Level 1 PSG. Technicians do not monitor the quality of the study information being collected overnight. Many devices are available on the market. Clinician stakeholders on the study (with no conflicts of interest) recommended the system chosen for study purposes.

#### **Product Acquisition:**

The screening tests are in the public domain thus no cost to the participant or study institutions. The diagnostic tests, supplies, and software were purchased using grant funding for study purposes.

#### **Potential Benefits and Risks to the Participants**

Protections Against Risk Implemented at Start of Trial: To minimize the risk of uncomfortable questions on assessments, participants are instructed during the informed consent process that they can decline to answer any question or discontinue participation at any point in the study. Participants will be informed in the consent form that they do not have to discuss any topics and engage in any procedures that they do not wish to during the assessment periods. In addition, participants are informed during the consent process they are free to stop an assessment at any time. Participants are also informed before each assessment period that they may refuse to answer any questions or procedures that make them feel uncomfortable. Any discomfort from wearing the sleep monitoring equipment (ACG or PSG), either physical or emotional, should be readily resolved with adjustments and repositioning. Continuous monitoring by a registered sleep technician during the PSG study will provide the participant with physical assistance for adjusting the equipment and with reassurance for the duration of the study. Any skin problems related to wearing the equipment, should be readily treated with skin lotion and repositioning the device. If the sleep assessment procedures are determined to be too physically or emotionally uncomfortable for the participant by either clinical or research staff, he/she may be administratively withdrawn from the study. All changes in the participant's medical status during an assessment will be communicated to clinical staff for follow up. Should the participant appear to become medically distressed during the course of an assessment, research staff will immediately contact the participant's clinical staff and study investigators for follow up. If research personnel discover new medical or emotional concerns during study assessments, the research staff member will promptly report this information to clinical staff and to study investigators for follow up. If, during the course of

the study, the patient is discovered to have sleep apnea or another sleep disorder, this information will be communicated to the participant's clinical staff for follow up.

All unanticipated problems and adverse events will be tracked by research staff and promptly reported to the study investigators and IRBs for appropriate resolution. An unanticipated problem is defined as any incident, experience, or outcome that is unexpected (in terms of nature, severity, or frequency) given the research procedures that are described in the protocol-related documents; possibly related to participation in the research; and suggests that the research places subjects or others at a greater risk of harm (including physical, psychological, economic, or social harm) than was previously known or recognized. Unanticipated problems will be promptly reported immediately to the site investigator and to the local IRB, as well as to the study Principal Investigators. An Unanticipated Problem Report form will be completed and returned to all regulatory institutions as soon as possible.

An adverse event (AE) is any unfavorable and unintended sign, symptom or disease temporally associated with a study procedure regardless of whether it is considered related to the procedure. A serious adverse event (SAE) is any untoward medical occurrence that 1) results in death, 2) is life-threatening, 3) requires inpatient hospitalization or prolongation of existing hospitalization, or 4) results in persistent or significant disability/incapacity. AEs may be graded as mild (no limitation of usual activities), moderate (some limitation) or severe (inability to carry out usual activities) and attributed according to the relationship to the study procedures as not related, possibly related, or related. A clinical event form will be completed in the case of any and all reported adverse events associated with the treatment procedures. Copies of these forms will be sent to the Principal Investigators. The original will be placed in the participant's study folder. The purpose of this procedure is to make certain all possible adverse events are examined to determine the proper action, if any, that needs to be taken. Mild and moderate AEs will be tracked and reported quarterly to the Principal Investigator. SAEs will be reported immediately to the site principal investigator and to the local IRB. An Adverse Event Report form will be completed and returned to all regulatory institutions as soon as possible. To protect confidentiality of data, all data will be maintained in a secure database on secure servers. Within the database and on all data collection forms, numbers will be used in place of names or other direct identifiers. Any hard copies of data collection forms and tools are kept in locked file cabinets. Only research staff members assigned to the project will have access to documents and computer databases. All investigators and research staff involved in the project will have completed online training in protection of human subjects. Research staff will not disclose the identity of a participant or any information regarding participation to anyone beyond legal parties who are privy to this information.

## **Methods**

**Study Design:** Prospective diagnostic clinical trial of comparative effectiveness of screening and diagnostic tools for sleep apnea.

**Study population and selection criteria:** Potential participants were consecutive patients enrolled in the TBI Model Systems (TBIMS) at six sites (Tampa FL, Seattle WA, Dallas TX, Columbus OH, Denver CO, and Philadelphia, PA) described earlier and over 19 months. Study inclusion/exclusion criteria for the TBI Model Systems and this trial are described in Table 1.63 The requirement of TBIMS enrollment at time of consent for the clinical trial was relaxed at study-month 11 to allow for earlier enrollment during rehabilitation but the clinical criteria remained unchanged.

**Recruitment Methods:** All participating sites received institutional review board approval for conduct of the study. Consecutive admissions were screened for eligibility. Participants who passed the first level of

screening (or their proxies) were consented and further screened for final eligibility including 1)  $\geq 2$  hours sleep/night based on actigraphy placement or nursing logs/report, and 2) medical stability (including no emergent medical issues precluding overnight PSG and minimal to no post-traumatic agitation, as assessed by the Agitated Behavior Scale). Once determined eligible, an overnight PSG study was conducted by a registered polysomnographic technician (RPSGT) in the participant's own bed. Within 72 hours of the PSG, questionnaire-based sleep apnea screening measures were completed with the participant and/or best source available using established TBIMS procedures by local staff blinded to PSG results. Sleep-related information during hospitalization was collected from the medical staff (snoring status, daytime sleepiness) or medical record (weight, height). The patient-reported outcome was the primary source of data. When data were missing due to the participant's inability to respond or with unknown responses, it was imputed using best source data if available otherwise was considered missing data.

Data collection and reporting: Demographic and pre-injury medical histories, and medical record abstraction were conducted by trained research assistants following the TBIMS protocol. Within 72 hours of the PSG, questionnaire-based sleep apnea screening measures were completed with the participant and/or best source available using established TBIMS procedures by local staff blinded to PSG results. Sleep-related information during hospitalization was collected from the medical staff (snoring status, daytime sleepiness) or medical record (weight, height). The patient-reported outcome was the primary source of data. When data were missing due to the participant's inability to respond or with unknown responses, it was imputed using best source data if available otherwise was considered missing data. Participants underwent simultaneous administration of Level 1 PSG (Philips Alice 6 LDx Diagnostic Sleep System with Philips Sleepware G3 version 3.8.1 software) and portable sleep study (i.e., HSAT using the Nox T-3 Monitor [Nox Medical Inc., Reykjavik, Iceland] and Noxturnal version 4.4.2 software). Fully attended Level 1 PSG was conducted in accordance with the American Academy of Sleep Medicine recommended procedures. Staff were instructed to allow participants their normal sleep period.

The lead center (James A. Haley Veterans' Hospital, Tampa, FL) served as a centralized scoring center for all sleep studies. All Level 1 PSG studies were masked and scored within seven business days of PSG completion with results subsequently databased and entered by research assistants. The Level 3 portable sleep studies were masked and scored in batches of 50+ studies approximately 3-6 months after completion and scoring of Level 1 PSG to assure blinding of portable study scoring from the Level 1 PSG results. All portable sleep studies were edited by the RPSGT; the automated software results were not used in analyses. Editing entailed setting start/stop recording times based on assessment of embedded actigraphy (reduction in movement) in the portable device and elimination of data during periods of absent valid waveforms for oximetric plethysmographic data, nasal pressure transducer data, and effort signal data.

### **Adverse Reactions**

None reported.

### **Reasons for withdrawal or termination**

No subjects were terminated from the study. No participant completely withdrew from the study. However, some study procedures were refused as described in corresponding publications for each aim.

### **Premature termination or suspension of the study**

Not applicable.

### **Sample Size Justification**

Power Analyses from Research Plan:

(Aim 1) To test the hypothesis for Aim 1, a paired-sample diagnostic analysis (estimated sensitivities/specificities) for each screening measure relative to the criterion standard, Level 1 PSG) was

performed using the same sample of patients. Prevalence of sleep apnea (as determined by Level 1 PSG) was conservatively estimated to be 30% using investigators' published reports of 37-39% prevalence in acute rehabilitation TBI samples. A two-sided McNemar's test, assuming a significance level of  $\alpha = 0.05$ , will have at least 80% power to detect a difference in sensitivities of 20% between screening measures for a sample size of 237. The power of the test will increase if the prevalence is higher than 30% (e.g., a prevalence of 35% would yield 87% power with 237 subjects and only require 203 subjects for 80% power). Furthermore, a sample size of 237 will have at least 80% power to detect a difference of 20% in sensitivities between screening measures in detecting sleep apnea.

(Aim 2) To test the non-inferiority hypothesis of the portable device for diagnosing sleep apnea, the non-inferiority of SE and SP (relative to SEH = 0.9 and SPH = 0.6, each within  $\Delta = 0.1$ ) were jointly tested at the significance level of  $\alpha=0.05$  by estimating the cross-product of two one-sided  $1-\alpha^*$  confidence intervals; SEH and SPH were selected a priori and were considered sufficiently large to obviate the need Level 1 PSG. For the purposes of the clinical trial, the study was powered to demonstrate non-inferiority of Level 3 sleep studies relative to fixed values of sensitivity (SE) and specificity (SP). Minimum sample sizes of 83 and 153 patients achieved at least 80% power to detect non-inferiority of SE to 90% and SP to 60% with a non-inferiority limit of  $\Delta = 0.1$ , using one-sided exact tests each at a 5% level of significance. In total, 214 subjects were available for analysis which yields 83.9% and 98.8% power, respectively, when testing the non-inferiority of SE and SP each at a 2.53% level of significance and maintaining a 5% level of significance when testing SE and SP jointly.

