Using individual significance levels of  $\alpha_{SE} = \alpha_{SP} = \alpha^* = 0.0253$  ensures that the overall significance region of the joint test of both SE and SP simultaneously remains no greater than  $\alpha = 0.05$ . If the lower confidence limits (LCL) from both  $1 - \alpha^* = 94.9\%$  confidence intervals are strictly above 0.8 for SE and 0.5 for SP, then a claim of non-inferiority of the portable diagnostic test would be established. Analyses were conducted for each AHI cutoff score (Total AHI  $\geq 5$ ,  $\geq 15$ , and  $\geq 30$ ) for the overall sample and by subgroups. The non-inferiority thresholds were chosen based on a prior systematic review showing estimates of SEs and SP for AHI  $\geq 5$  were 0.96 (95% CI = 0.90, 0.98) and 0.76 (95% CI = 0.63, 0.85), respectively, across varying OSA prevalence rates. Based on the lower bounds of these 95% confidence intervals (rounded to the nearest 10th), 90% SE and 60% SP with a delta of 0.1 were selected for declaration of non-inferiority.

3. Pepe MS. *The statistical evaluation of medical tests for classification and prediction*. 2003; Oxford University Press, New York.

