(Aim 2: Hypothesis 2.1): *Level 3 portable polysomnography with greater consumer accessibility will be equivalent (non-inferior) to the less accessible Level 1 polysomnography in determining presence of sleep apnea in TBI patients undergoing inpatient rehabilitation.* Justification of Assumptions/Power Estimate: To test hypothesis 2.1, the sensitivity (SE) and specificity (SP) of Level 3 PSG (compared to Level 1 PSG, the reference gold standard) will each be estimated and compared to fixed hypothesized rates of SE and SP considered sufficiently large enough to potentially obviate the need for Level 1 PSG. Based on a review of the literature and consensus among the investigators in this study, SE and SP no worse (non-inferior) to 90% and 60%, respectively, are considered sufficiently large enough. To test for non-inferiority of the SE to 90% and the SP to 60%, a non-inferiority threshold of $\Delta = 0.1$ is assumed for both measures. A sample size of at least 83 patients is necessary to achieve a minimum of 80% power to test the non-inferiority of the SE to 90% (assuming $\Delta = 0.1$ and $\alpha = 0.05$). A sample size of at least 153 patients is necessary for a minimum of 80% power to test the non-inferiority of the SP to 60% (assuming $\Delta = 0.1$ and $\alpha = 0.05$). Thus, a total of 153 subjects is required to sufficiently power both non-inferiority hypotheses. Analytic Plan: To test hypothesis 2.1, the sensitivity (SE) and specificity (SP) of Level 3 PSG (compared to Level 1 PSG, the reference gold standard) will each be estimated and compared to fixed hypothesized rates of SE and SP of 90% and 60%, respectively, considered sufficiently large enough. Level 1 PSG (reference) diagnosis of sleep apnea will be made based on $AHI \geq 5$. Level 3 PSG (test) diagnosis will be made based $AHI \geq 5$. A cross-tabulation of Level 3 PSG (positive/negative) versus Level 1 PSG (positive/negative) will be constructed and standard measures of diagnostic accuracy will be estimated along with 95% confidence intervals (i.e., sensitivity, specificity, positive and negative predictive values, and diagnostic accuracy). To test for non-inferiority of the SE to 90% and the SP to 60%, a non-inferiority threshold of 0.1 is assumed. If the lower bound on the 95% confidence interval for SE is strictly above 80% and the lower bound on the confidence interval for SP is strictly above 50% then non-inferiority of Level 3 PSG (compared to Level 3 PSG) can be established. All analyses will be performed using SAS v.9.4 (SAS Institute Inc., Cary, NC).

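### Aim 2 power is given test by test, but non-inferiority needs sensitivity and specificity both to pass; the joint power is never stated and is well below 80% at the plan's own assumptions

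*Protocol*

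**What the plan says.** The Protocol's Sample Size Justification for Aim 2 says "Minimum sample sizes of 83 and 153 patients achieved at least 80% power to detect non-inferiority of SE to 90% and SP to 60" per cent, "using one-sided exact tests each at a 5% level of significance". Its next statement concerns the 214 patients available for analysis: power of 83.9% and 98.8% for SE and SP respectively, "each at a 2.53% level of significance and maintaining a 5% level of significance when testing SE and SP jointly".

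The Protocol's Statistical Analysis Plan section (Aim 2, joint test) sets one decision with two conditions. If both lower limits "are strictly above 0.8 for SE and 0.5 for SP, then a claim of non-inferiority of the portable diagnostic test would be established".

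The SAP (Aim 2, Hypothesis 2.1) uses the same targets ("SE and SP no worse (non-inferior) to 90% and 60%, respectively, are considered sufficiently large enough") and the same margin ("a non-inferiority threshold of 0.1 is assumed"). It also requires both lower bounds to pass, using 95% confidence intervals. It gives 83 and 153 as the sizes for the two tests and then says: "Thus, a total of 153 subjects is required to sufficiently power both non-inferiority hypotheses".

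Neither document states the probability that both conditions are met.

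**The concern.** The type I error is handled jointly: the Protocol sets 2.53% per test so that the joint level stays at 5%. Power is not handled in the same way. Each figure is the chance that one condition passes, while the trial's conclusion needs both. The Protocol introduces these figures as the basis on which the study was powered for non-inferiority, and the SAP says that one total covers both hypotheses. A reader is therefore likely to take about 80% as the chance of reaching the conclusion when the device truly has SE 0.90 and SP 0.60. If the real chance is much lower, a failed joint test could be taken as evidence against portable testing when it mostly reflects sample size.

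**Working it through.** **Inputs.** Assumed true rates are SE 0.90 and SP 0.60; with margin 0.1 the null values are 0.80 and 0.50 (both documents). The per-test level is one-sided 5% for the minimum sizes and 2.53% for the joint test (Protocol). The SAP's 95% intervals, if two-sided, imply 2.5% per side, which is practically the same as 2.53%. Prevalence is given only for Aim 1 (30%, from reports of 37-39%). Its use for Aim 2 is an assumption made here.

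**1. Reproduce 83 and 153.** By the normal approximation, n = [(z(1-α)·√(p0·q0) + z(0.80)·√(p1·q1)) / (p1 - p0)]².

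- SE: [(1.645 × 0.400 + 0.842 × 0.300) / 0.1]² = 82.9, rounded up to 83.
- SP: [(1.645 × 0.500 + 0.842 × 0.490) / 0.1]² = 152.5, rounded up to 153.

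Both match. The text names exact tests; strict exact binomial tests give 79.5% at 83 (reject at 73 or more) and 76.2% at 153 (reject at 88 or more).

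**2. Joint power at 83 positives and 153 negatives.** Per-test power = Φ[(p1 - p0 - z(1-α)·√(p0·q0/n)) / √(p1·q1/n)]. The two estimates come from different patients, so the powers multiply.

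| Level per test | SE power | SP power | Joint | Exact joint |
|---|---|---|---|---|
| 5% | 0.801 | 0.801 | 64% | 0.795 × 0.762 = 61% |
| 2.53% | 0.667 | 0.702 | 47% | 0.684 × 0.650 = 44% |

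This case needs 83 + 153 = 236 patients, split exactly that way.

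**3. The SAP total of 153.** A patient is either Level 1 positive or Level 1 negative, so 153 must be divided. Searching all splits, the highest joint power is about 42% at 5% each and 26% at 2.53% each. Even counting all 153 in both denominators, which is impossible, gives only 0.973 × 0.801 = 78% at 5%.

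**4. The N = 214 figures.** With n = 214 in both formulas at 2.53%, SE power is 98.8% and SP power is 83.9%. These are the Protocol's two numbers in the opposite order. They therefore reproduce only if all 214 patients count in both denominators, and the labels appear swapped. Their product is 0.839 × 0.988 = 82.9%.

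Dividing 214 by prevalence, at 2.53% each:

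| Prevalence (assumed) | Positives / negatives | SE power | SP power | Joint |
|---|---|---|---|---|
| 30% | 64 / 150 | 0.524 | 0.693 | 36% |
| 37% | 79 / 135 | 0.639 | 0.647 | 41% |
| 39% | 83 / 131 | 0.667 | 0.634 | 42% |

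Over every possible split of 214, joint power is at most about 44% at 2.53% each and about 60% at 5% each. These ceilings need no prevalence assumption.

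**5. Sensitivity to the assumed truth.** The Protocol takes 0.90 and 0.60 from the lower confidence bounds of a review whose point estimates were SE 0.96 and SP 0.76. At those estimates, exact joint power with 64 positives and 150 negatives at 2.53% each is about 98.6%.

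**The case against.** The best reply is that the Protocol sentence on 83 and 153 makes no joint claim. It gives two sizes for two tests and says that each is at 5%. That stands: under the normal approximation it is a correct per-test statement. A reader might infer that the sentence is false, or that 64% is the power of the claim the trial tested. The documents support neither. The 64% belongs to a 236-patient design at 5% per test, which is not the SAP's total, the analysed number or the Protocol's joint-test level.

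A second reply is that the Protocol's own figures for 214 patients multiply to 82.9%, so multiplying creates no shortfall. The multiplication is right, but the inputs are not usable because they place every patient in both denominators.

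A third reply is that the Protocol's 94.9% interval, if read as a one-sided limit, implies about 5.1% per test. It is also true that a rule requiring both tests to pass does not itself require the level to be divided. On that reading the 83/153 figure returns to about 64%, and the ceiling for 214 patients is about 60%. Both are still below 80%.

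Finally, power is high if the true accuracy is near the review's estimates, enrolment is complete, and the decision rests on confidence limits. All of this stands. It limits the consequence but does not supply the missing figure.

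**Conclusion.** The point holds as an unstated joint power, not as an error in the 83 and 153 calculation. If the device truly has SE 0.90 and SP 0.60, the probability of the non-inferiority claim is about 36-42% for 214 patients at 30-39% prevalence and 2.53% per test, and no split of 214 exceeds about 44%. The SAP's statement that 153 in total suffices for both tests cannot be supported: the ceiling is about 42% at 5% each and 26% at 2.53% each.

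These results rest on the normal approximation (exact values are close), on SE and SP coming from disjoint patients, and, for the 36-42% range, on borrowing the Aim 1 prevalence. A reader might go further and infer that the trial's conclusion is invalid. That does not follow, because planning power does not enter the decision rule and is much higher if the true accuracy exceeds 0.90 and 0.60.

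**What to change.** In the Protocol's Sample Size Justification and the SAP's Hypothesis 2.1:

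- Label 80%, 83.9% and 98.8% as per-test figures. Check the order of the last two and state the denominators they assume.
- Add the joint power at the alpha actually used, with positives and negatives derived from a stated prevalence. For N = 214 at 2.53% each and 30-39% prevalence this is about 36-42%.
- Remove the SAP sentence that 153 patients in total power both tests.
- Note that power is higher if the true accuracy exceeds 0.90 and 0.60, for example at the review estimates of 0.96 and 0.76.

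A sentence on how a failed joint test would be interpreted is optional. The change is to wording only and needs no extra patients. Its cost is a less favourable stated power.

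### The Aim 2 sample sizes of 83 and 153 come from a normal approximation; the exact test the protocol names gives 76.2% power for specificity, not at least 80%

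*Protocol*

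**What the plan says.** The protocol, under Sample Size Justification (Aim 2), sets the hypothesised values and margin as "relative to SEH = 0.9 and SPH = 0.6, each within" 0.1. It then states: "Minimum sample sizes of 83 and 153 patients achieved at least 80% power", and names the method: "using one-sided exact tests each at a 5% level of significance". The same paragraph reports 83.9% and 98.8% power, respectively, for sensitivity (SE) and specificity (SP) with 214 subjects at a 2.53% level for each measure.

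The null values follow from the decision rule in the protocol's Statistical Analysis Plan section. Non-inferiority is claimed if the lower confidence limits "are strictly above 0.8 for SE and 0.5 for SP".

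The SAP (Aim 2, Hypothesis 2.1, power estimate) gives the same sizes. For specificity it says: "A sample size of at least 153 patients is necessary for a minimum of 80% power", with alpha 0.05. It does not say whether the test is exact or approximate.

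**The concern.** An exact binomial test can reject only at whole numbers of successes, so its attained level usually lies below the nominal 5% and its power below the normal-approximation value. Sizes that only just reach 80% under the approximation may therefore miss 80% under the exact test. If so, the protocol credits the named test with power it does not have, and a reader who repeats the calculation as described gets a different answer.

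Specificity is the measure to watch. The Aim 2 claim needs both limits to be met, and specificity sets the larger of the two sizes.

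**Working it through.** **Inputs, all printed in the documents.** SE: null p0 = 0.8, alternative p1 = 0.9. SP: p0 = 0.5, p1 = 0.6. One-sided level 5% for the minimum sizes and 2.53% for the 214-subject figures. Target power 80%.

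**Step 1: reproduce 83 and 153.** The one-sample normal approximation, with the null variance in the critical value and the alternative variance in the power term, is

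n = [(z(0.95) × √(p0(1−p0)) + z(0.80) × √(p1(1−p1))) / 0.1]², with z(0.95) = 1.645 and z(0.80) = 0.842.

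- SE: [(1.645 × 0.4 + 0.842 × 0.3) / 0.1]² = 82.89, rounded up to 83.
- SP: [(1.645 × 0.5 + 0.842 × 0.490) / 0.1]² = 152.46, rounded up to 153.

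Power at those sizes is Φ[(0.1√n − z × √(p0(1−p0))) / √(p1(1−p1))]: 80.06% for SE and 80.13% for SP. Both printed sizes are matched.

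**Step 2: apply the test the protocol names.** Take the smallest r with P(X ≥ r | n, p0) ≤ 0.05. Power is P(X ≥ r | n, p1).

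| Measure | n | Reject at | Attained level | Exact power |
|---|---|---|---|---|
| SE | 83 | ≥ 73 | 4.1% | 79.5% |
| SP | 153 | ≥ 88 | 3.7% | 76.2% |

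Lowering the cut-off by one success would give 87.7% (SE) and 80.9% (SP), but the levels would be 7.6% and 5.3%, both above 5%.

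**Step 3: sizes that reach 80% exactly.** Exact power is saw-toothed in n.

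- SE first reaches 80% at n = 82 (80.6%), dips below at 83, and stays at or above 80% from 94.
- SP first reaches 80% at n = 158 (80.6%) and stays there from 169.

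**Step 4: the 214-subject figures.** Use the same approximation with n = 214 and z(0.9747) = 1.955.

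- SE: Φ[(1.463 − 1.955 × 0.4) / 0.3] = Φ(2.27) = 98.8%.
- SP: Φ[(1.463 − 1.955 × 0.5) / 0.490] = Φ(0.99) = 83.9%.

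These are the protocol's two values in the opposite order. The exact test, with 214 as the denominator for each measure, gives 98.6% for SE (reject at ≥ 183) and 83.2% for SP (reject at ≥ 122).

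**Step 5: denominators, as an illustration only.** SE is estimated in PSG-positive patients and SP in PSG-negative patients, so 214 cannot be the denominator for both. The documents do not print the split. Under Aim 1 they plan on 30% prevalence and cite reports of 37–39%.

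- At 30%, 214 × 0.30 ≈ 64 positives and 150 negatives. Exact power at 2.53% is about 54% for SE (reject at ≥ 58) and 66% for SP (reject at ≥ 88).
- At 39%, 214 × 0.39 ≈ 83 positives and 131 negatives. Exact power is about 68% for SE (reject at ≥ 74) and 58% for SP (reject at ≥ 78).

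**The case against.** Much of the case on the other side stands.

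- **Sensitivity is trivial.** The shortfall is 0.5 point, and 83 misses 80% only because of the saw-tooth; 82 would pass. A reader might infer that both sizes are materially too small. Only specificity is visibly short, by 3.8 points, with 153 lying 5 below the first qualifying size.
- **The SAP is not wrong on this ground.** A reader might carry the error across because the SAP repeats 83 and 153. It names no exact test, and the approximation supports both sizes.
- **The minimum sizes do not decide anything now.** Enrolment is complete, 214 subjects were available, and the protocol's decision rule uses confidence limits at 2.53% for each measure rather than the 5% tests behind 83 and 153. With 214 as the denominator for each measure, exact power still exceeds 80% for both and differs from the printed values by less than one point. A reader might infer from the word exact alone that Aim 2 was underpowered; the documents do not support that.
- **94 and 169 are a convention.** At least 80% power at a fixed size requires only 82 and 158.

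What does not fall is the statement itself. The protocol names a test and a power that do not go together, and rounding cannot rescue specificity without breaching 5%.

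**Conclusion.** The protocol's claim of at least 80% power with exact tests is wrong as written. The size is 76.2% against 80% for specificity, and a negligible 79.5% against 80% for sensitivity. All four printed Aim 2 numbers (83, 153, 83.9%, 98.8%) match the normal approximation, so the likeliest explanation is that the calculation was mislabelled. This rests only on printed inputs and on reading the exact test as the ordinary one-sided binomial test.

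The reversed 83.9% and 98.8% are a separate slip in the same paragraph. As printed, the measure with the thinner margin, specificity, appears to have near-certain power.

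The point does not alter the decision rule or any result. The 54–68% and 58–66% powers in Step 5 depend on an assumed prevalence and come from the choice of denominator, not from exact versus approximate testing. They show why restated power should not use 214 for both measures; they do not show what the trial's power was.

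**What to change.** In the protocol's Sample Size Justification, Aim 2:

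1. Either describe the calculation behind 83 and 153 as a normal approximation, which leaves the sizes and the 80% claim intact, or keep the word exact and restate the powers as 79.5% for sensitivity at 83 and 76.2% for specificity at 153. If exact sizes are also wanted, say which convention is used: first reaching 80% (82 and 158) or staying there (94 and 169).
2. Correct the order of the 214-subject figures to 98.8% for sensitivity and 83.9% for specificity, and name the method.
3. Base any restated power on the number of PSG-positive patients for sensitivity and PSG-negative patients for specificity, and print those counts.

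The SAP's Aim 2 power paragraph needs no correction on this ground, only agreement with whichever method the protocol states.

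The cost is a few sentences. No patients are added and no analysis changes. If the exact wording is kept, the stated planning power becomes slightly less favourable. Restating power on the PSG-positive and PSG-negative counts may lower it further.
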